### 4.1.3. Implementation Assessments

Implementation outcomes align with the study's objectives and Proctor and colleague's [Proctor, 2011] implementation outcome recommendations. The administration of assessments for SSPs and PSPs, including facilitation calls and FRAME-IS, is outlined in **Table 3**. Baseline assessments should be completed prior to the enrollment of first participant. Implementation information may also be gathered from or about site staff members who are administering APRETUDE to non-PSPs.

One or more interim analysis will be conducted to provide early evaluation of the implementation science primary and key secondary objectives. The timing of the interim/s will be based on when a sufficient number of SSPs and/or PSPs questionnaires and interviews have been completed.

**Table 3 Implementation Assessments**

Outcome	Assessment Level	Measurement	OLI/DTI Time point
Feasibility-Overall	Staff Study Participants	FIM	BL, M5, M13
		Staff ISQ	BL, M5, M13
		SSI	M5, M13
	Patient Study Participants	FIM	M13(OLI)/M12(DTI)
		Patient ISQ	BL, M7(OLI)/M6(DTI), M13(OLI)/M12(DTI)
		SSI	BL, M7(OLI)/M6(DTI), M13(OLI)/M12(DTI)
Acceptability-Overall	Staff Study Participants	AIM	BL, M5, M13
		SSI	M5, M13
Feasibility - Telehealth	Staff Study Participants	FIM	BL, M5, M13
		SSI	M5, M13
		Staff ISQ	BL, M5, M13
	Patient Study Participants	FIM	BL, M7(OLI)/M6(DTI), M13(OLI)/M12(DTI)
		SSI	BL, M7(OLI)/M6(DTI), M13(OLI)/M12(DTI)
		Patient ISQ	BL, M7(OLI)/M6(DTI), M13M13(OLI)/M12(DTI)
Acceptability - Telehealth	Staff Study Participants	AIM	BL, M5, M13
		SSI	M5, M13
		Staff ISQ	BL, M5, M13
	Patient Study Participants	AIM	BL, M7(OLI)/M6(DTI), M13(OLI)/M12(DTI)
		SSI	BL, M7(OLI)/M6(DTI), M13M13(OLI)/M12(DTI)
	Patient ISQ	BL, M7(OLI)/M6(DTI), M13(OLI)/M12(DTI)	
Acceptability – Cabotegravir LA	Patient Study Participants	AIM	BL, M7(OLI)/M6(DTI), M13(OLI)/M12(DTI)

Outcome	Assessment Level	Measurement	OLI/DTI Time point
		SSI	BL, M7(OLI)/M6(DTI), M13(OLI)/M12(DTI)
		Patient ISQ	BL, M7(OLI)/M6(DTI), M13(OLI)/M12(DTI)
Fidelity	Patient Study Participants	Adherence to Target date ( $\pm 7$ days), eCRF	Monthly
		Patient ISQ	BL, M7(OLI)/M6(DTI), M13(OLI)/M12(DTI)
		SSI	BL, M7(OLI)/M6(DTI), M13(OLI)/M12(DTI)
	Staff Study Participants	Staff ISQ	BL, M5, M13
		SSI	BL, M5, M13
		# clinical staff-initiated assessments/ # eligible pts	Monthly
	Cross Study 	Composite measure*: • adherence to target date • assessments given • missed appointments	BL-M13
Reach	Staff Study Participants	# pts receiving 1st injection / #eligible pts based on assessments	Monthly
Awareness	Staff Study Participants	Assessment tool	Monthly
		Staff ISQ	BL, M5
		SSI	BL, M5
	Patient Study Participants	Assessment tool	BL
		Patient ISQ	BL
Uptake	Staff Study Participants	Assessment tool	Monthly
		Clinic administrative records	Monthly
		Staff ISQ	BL, M5, M13
	Patient Study Participants	Assessment tool	Monthly
		Patient ISQ	BL
Persistence, Retention	Staff Study Participants	Assessment tool	Monthly
		Clinic administrative records	Monthly
		Adherence to Target date ( $\pm 7$ days), admin records	Monthly
		Staff ISQ	BL, M5, M13
	Patient Study Participants	Adherence to Target date ( $\pm 7$ days), eCRF	Monthly
Process evaluation of implementation		Patient ISQ	M7(OLI)/M6(DTI), M13(OLI)/M12(DTI)
		SSI	M7(OLI)/M6(DTI), M13(OLI)/M12(DTI)
	Staff Study Participants,	SSI	BL, M5, M13

Outcome	Assessment Level	Measurement	OLI/DTI Time point
strategies and toolkits			
	Patient Study Participants	SSI	BL, M7(OLI)/M6(DTI), M13(OLI)/M12(DTI)
Perceptions, barriers & facilitators	Staff Study Participants,	SSI, Staff ISQ	BL, M5, M13
	Patient Study Participants	SSI, Patient ISQ	M7(OLI)/M6(DTI), M13(OLI)/M12(DTI)

Abbreviations: FIM: Feasibility of Intervention Measure; AIM: Acceptability of Intervention Measure; SSI: Semi-Structured Interviews; M: Month; DTI: Direct to Injection; OLI: Optional Oral Lead In

\*Composite measure to be developed in consultation with stats; example of measures provided

Measures taken from both SSPs and PSPs across the study implementation period; to be further refined

**4.1.3.1. Timepoint Definitions for Completion of Questionnaires and Interviews****PSPs:**

- PSPs who are started on oral Cabotegravir PrEP as optional OLI will receive their first dose of oral CAB in Month 1. PSPs who are started on APRETUDE injections (direct to injection) will receive their first dose of APRETUDE injection in Month 1.
- Each administration of APRETUDE injection will be categorized by the sequential number, e.g., Dose 1 visit (first injection), Dose 2 visit (second injection); and the corresponding Study Month will be recorded.
- Baseline IS assessment is defined as the first assessment taken on or before receiving Dose 1 of APRETUDE injection. Baseline questionnaires should be completed within two weeks of or on their Dose 1 visit and before receiving the first APRETUDE injections.
- For each PSP, the last APRETUDE injection is to occur at the last study visit.
- All study visits, including those where questionnaires and/or interviews are administered at M7(OLI)/M6(DTI) and M13(OLI)/M12(DTI), will be anchored off of each PSP M1, so it reflects months in study, regardless of what dose they are on and regardless of whether they have missed any injections and received oral CAB tablets for PrEP.
- Approximately 3 PSPs per site will participate in SSIs; number of SSIs might vary by site. Participants will be purposely sampled for interviews based on demographic characteristics, such as race/ethnicity, prior PrEP use.
- Interviews should be conducted with all PSPs who discontinue participation within one month of discontinuation, when possible.

**SSPs:**

- Baseline IS assessment is defined as the first assessment taken prior to administering the first APRETUDE injection at each site. Baseline questionnaires should be completed by all SSPs within 1-2 weeks of the site's initiation.
- For sites with both OLI and DTI participants, M4/M5 visit will be defined when at least 1 participant, at their respective site, has completed their M4(DTI)/M5(OLI) study visit (Dose 3 visit), respectively, whichever comes first. M12/M13 visit will be defined after at least 1 participant, at their respective site, has completed their M12(DTI)/M13(OLI) study visit (Dose 7 visit), whichever comes first.
  - Questionnaires and/or interviews can be completed within 3 weeks of the respective study visits.
- For a site with only DTI patients, the visits will be defined at M4 and M12, respectively. For a site with only OLI patients, the visits will be defined at M5 and M13, respectively.

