## 2. OBJECTIVES AND ENDPOINTS

• Objectives	• Endpoints
• Primary	
• To evaluate feasibility of dynamic implementation (DI) compared to routine implementation (RI) for APRETUDE administration.	• Staff study participants' (SSPs) mean Feasibility of Intervention Measure (FIM) score at M13  .
• Secondary	•
• To evaluate change in feasibility of RI and DI for APRETUDE administration	• Change from baseline in SSPs' FIM score at M5 and M13. • SSPs perceptions of facilitators and barriers to RI and DI and overall implementation of PrEP into routine care assessed through M13.
• To evaluate feasibility and acceptability of APRETUDE for MSM and TGM.	• Patient Study Participants' (PSPs) mean FIM and Acceptability of Intervention Measure (AIM) scores as well as implementation science questionnaire (ISQ) responses at BL, M7(OLI)/M6(DTI) and M13(OLI)/M12(DTI). • Change from baseline in PSPs' AIM and FIM scores as well as ISQ responses FIM score at M7(OLI)/M6(DTI) and M13(OLI)/M12(DTI). • PSPs perception of facilitators and barriers to feasibility and acceptability of APRETUDE through M13(OLI)/M12(DTI).
• To evaluate feasibility and acceptability of telehealth delivery for APRETUDE administration by clinical staff.	• SSPs' mean FIM and AIM scores as well as ISQ responses for telehealth delivery at BL, M5 and M13. • Change from baseline in SSPs' FIM and AIM score as well as ISQ responses for telehealth delivery at M5 and M13 .

• Objectives	• Endpoints
	
 
• PSPs' mean FIM and AIM scores as well as ISQ responses for telehealth delivery at BL, M7(OLI)/M6(DTI) and M13(OLI)/M12(DTI)
 
• Change from baseline in PSPs' FIM and AIM scores as well as ISQ responses for telehealth delivery at M7(OLI)/M6(DTI) and M13(OLI)/M12(DTI).
 
• SSPs and PSPs perception of facilitators and barriers to feasibility and acceptability of telehealth use through M13 and M13(OLI)/M12(DTI) respectively.
 

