### 3.3.2. SSPs

SSPs will complete assessments as outlined in [ANNEX 1](#) and agree to data privacy requirements prior to the completion of study assessments. Assessments will include questionnaires and interviews at baseline, M5 and M13; baseline questionnaires with SSPs should be completed prior to the enrolment of the first participant at their site, which might vary by site depending on whether the first PSP started CAB PrEP with or without optional OLI. They will also participate in monthly FRAME-IS assessments. Sites in the DI arm will participate in quarterly group and monthly one-on-one facilitation calls.

The PrEP provider at the site will manage and remain responsible for all clinical aspects of the PSPs enrolled at the site during the study.

- During the screening period, the site will obtain the PSP's informed consent and confirm inclusion and exclusion criteria prior to enrolling in the study/M1. The site will also complete demography and vital signs and required labs per clinical local standard of care.
- (See SoA for specific laboratory test results that should be documented in the eCRF, e.g., HIV testing results and any positive STI clinical diagnoses (defined for this study as syphilis (any stage), gonorrhea, chlamydia, or trichomonas) at Screening and at any time point during the study, laboratory abnormalities associated with AEs leading to study discontinuations, positive pregnancy test results). The site will explain to the PSPs that medical records may be requested from other medical facilities to support complete reporting of SAEs or other events if they occur during the study.
- For PSPs diagnosed with incident HIV-1 infections (defined as newly diagnosed HIV infection following enrolment and during the study), the site may perform additional tests, including but not limited to HIV-1 viral load, CD4 count, genotype/phenotype tests, and recency assays, and initiate antiretroviral therapy (ART) as per the site's standard of care. See SoA for collection of available results as well as the start date of ART and classes of ART regimen used for PSPs with incident HIV-1 infection.
- The PrEP provider at the site will prescribe CAB tablets for PrEP to PSPs who will receive optional OLI and administer APRETUDE IM injections as per approved prescribing information.

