#### 4.1.1. Routine Implementation

The RI arm will evaluate the feasibility of APRETUDE delivery without implementation supports. Sites randomized to RI will have access to the standard toolkits for providers and patients that will be available for APRETUDE to use as needed. An overview of example materials contain in the toolkits is provided in [Table 1](#). Detail information on the toolkits is given in the SRM. SSPs in the RI arm will participate in study training, FRAME-IS assessments and implementation monitoring.

- **Study Training:** In preparation for the study, all SSPs and other relevant site staff will receive study training including information on safety and effectiveness of APRETUDE, study procedures, and information and/or training on implementation strategies. Study training requirements will be described in the study training plan and evidence of training will be filed in the Investigator Site File (ISF). Initial study training will be covered in the Investigator meeting, other virtual sessions, via on demand learning or and at the site initiation visits. SSPs should complete all study training applicable to their role.
- **FRAME-IS Assessments:** SSPs in the RI arm most knowledgeable of the study, clinic operations and modifications will participate in monthly FRAME-IS assessments, which are administered via email and takes maximum 15 minutes to complete. All SSPs will be asked to complete the FRAME-IS in order to understand implementation from the perspective of the different roles. The Framework for Reporting Adaptations and Modifications to Evidence-based Implementation Strategies (FRAME-IS) provides a systematic way of documenting and tracking modifications to implementation strategies in traditional healthcare settings, allowing for a better understanding of how the strategies influence outcomes [[Miller](#), 2021]. The assessments will provide understanding of implementation challenges and successes as well as modifications made, if any, to overcome identified challenges at each clinical site.

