**Staff Study Participants: Month 1 questionnaires should be completed prior to the first participant is enrolled**

Baseline IS assessment is defined as the first assessment taken prior to administering the first IM injection to the first participant at each site.

Baseline questionnaires should be completed by all SSPs within 1-2 weeks of their site initiation.

For sites with both OLI and DTI participants, M4/M5 visit will be defined by the target date when at least 1 participant, at their respective site, has completed their M4(DTI)/M5(OLI) study visit (Dose 3 visit), respectively, whichever comes first. M12/M13 visit will be defined by the target date when at least 1 participant, at their respective site, has completed their M12(DTI)/M13(OLI) study visit (Dose 7 visit), whichever comes first.

If the site only has DTI patients, the visits will be defined at M4 and M12, respectively. If a site has only OLI patients, the SSP assessment follows the OLI SOA in [ANNEX 2](#).

Interim and final SSP questionnaires and/or interviews can be completed within 3 weeks prior to or 3 weeks after study visits.

Implementation facilitation, implementation monitoring, and FRAME-IS can begin after baseline questionnaires have been completed by all SSPs. Sexual Health Assessment and aggregate clinic PrEP-related data collection can start prior to participant enrolment.

SSP Questionnaires	X				X									X	X	At least 1 participant must include an SSP who prescribes APRETUDE.
SSP Interviews					X									X	X	

Procedure 	Screening/ Enrollment Up to 90 days 	Treatment Period  Month(M)/Dose(D)												E.D. 	Notes
		M1	M2	M3	M4	M5	M6	M7	M8	M9	M10	M11	M12		
		D1  visit	D2 visit		D3 visit		D4 visit		D5 visit		D6 visit		D7 visit		
Implementation Facilitation Calls (DI Arm Only)		X	X	X	X	X	X	X	X	X	X	X	X		Group - Quarterly: At least 1 consistent SSP knowledgeable of implementation. One-on-one - monthly: At least 1 consistent SSP knowledgeable of implementation.
Implementation Monitoring (RI Arm Only)		X	X	X	X	X	X	X	X	X	X	X	X		At least 1 consistent SSP knowledgeable of implementation to participate.
FRAME-IS Questionnaire		X	X	X	X	X	X	X	X	X	X	X	X		All SSPs in the RI and DI arms will be asked to complete.
Sexual Health Assessment (DI Arm Only)	X	X	X	X	X	X	X	X	X	X	X	X	X		

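### Staff baseline has two inconsistent cut-offs, and the DI-only Sexual Health Assessment is not held until baseline is complete, so the baseline for the secondary change endpoints can follow the start of a DI component

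*Protocol*

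**What the plan says.** Two different events limit the SSP baseline.

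- **First participant enrolled.** Section 3.3.2: "baseline questionnaires with SSPs should be completed prior to the enrolment of the first participant at their site". Section 4.1.3: "Baseline assessments should be completed prior to the enrollment of first participant". The headers of the staff blocks in Annexes 1 and 2 say the same of the Month 1 questionnaires.
- **First injection.** Section 4.1.3.1 defines baseline in these terms: "Baseline IS assessment is defined as the first assessment taken prior to administering the first APRETUDE injection at each site". Below their headers, both annexes define it as the "first assessment taken prior to administering the first IM injection to the first participant at each site". Each annex therefore carries both limits.

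A timing target sits alongside: "Baseline questionnaires should be completed by all SSPs within 1-2 weeks of the site's initiation".

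The staff blocks of both annexes allow facilitation, monitoring and FRAME-IS to begin once all SSPs have completed the baseline questionnaires. The next sentence reads: "Sexual Health Assessment and aggregate clinic PrEP-related data collection can start prior to participant enrolment". It carries no such condition. The schedules label the Sexual Health Assessment as DI arm only and mark it in the screening column. Table 2 lists reach, fidelity, feasibility and acceptability as its outcomes.

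The first secondary objective in Section 2 is measured by "Change from baseline in SSPs' FIM score at M5 and M13". Change in SSP AIM and ISQ is also secondary.

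**The concern.** A change score is a clean measure of what a strategy did only if the baseline precedes the strategy. The protocol accepts that principle, because it makes facilitation wait for the baseline questionnaires. It does not apply it to another DI component that staff help to deliver and that the protocol itself expects to bear on feasibility. It also gives two answers to which forms count as baseline, and the looser one allows more time for that component to be in use.

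If some DI staff give their baseline rating after the tool is running, any effect it has already had on their view of feasibility is subtracted from their later change. RI clinics do not have the tool, so the distortion falls on one arm. This affects the DI arm's own change at M5 and M13 and any comparison of change between arms.

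**Working it through.** **1. Do the two limits accept different forms?** Let E be enrolment of a site's first participant and J the first injection there.

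- Direct to injection: Annex 1 allows screening/enrolment on the same date as the first injection, so J − E can be 0.
- Oral lead-in: Section 3.3.1 sets about 1 month, at least 28 days, of tablets before the first injection. If all early participants at the site take the lead-in, J − E is at least 28 days.

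The 28-day figure needs two conditions: no direct-to-injection participant is injected in between, and, on the literal wording of Section 4.1.3.1, nobody else at the site is either. Where they hold, a form completed between E and J is baseline under the Section 4.1.3.1 definition and too late under Sections 3.3.2 and 4.1.3.

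**2. Can a DI component come before an accepted baseline?**

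| Component | Arm | Must wait for all SSP baselines? |
|---|---|---|
| Facilitation | DI | Yes |
| Monitoring | RI | Yes |
| FRAME-IS | Both | Yes |
| Sexual Health Assessment | DI | No; may start before E |

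Under the looser limit, a form completed between E and J can follow the tool's launch. Under the stricter limit the order is still open: the tool and the baseline may both come before E, and nothing puts the baseline first. Reconciling the cut-off alone would therefore not close the gap.

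**3. What does that do to a change score?** Suppose the tool has already moved mean DI baseline by b, and RI by 0. Then:

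observed DI change = change from a clean baseline − b

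observed DI − RI difference in change = clean difference − b

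The error is exactly b, and its sign is the sign of b.

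**4. Is there a yardstick?** The nearest is the detectable difference in Section 5.2 (30 RI and 60 DI staff, 80% power; two-sided alpha of 0.05 is my assumption, as Sections 5.1 and 5.2 state none).

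- d = (1.960 + 0.842) × √(1/30 + 1/60) = 0.627; a noncentral t calculation gives 0.633. The protocol's 0.63 is reproduced.
- 0.63 × 0.59 = 0.37, as stated.

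Purely for scale, let the clean difference in change be 0.37 and let a share f of it be present at baseline. At f = 0.10 the observed difference is 0.90 × 0.37 = 0.333; at f = 0.50 it is 0.50 × 0.37 = 0.185. Both values of f are assumptions. The 0.37 is a difference in Month 13 means, not in changes, and clustering is ignored, as it is in Section 5.2. These figures show how the error passes through; they do not estimate it.

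**The case against.** The strongest reply is that the rules can all be met together. A form completed within the 1-2 week target and before first enrolment satisfies every one, and Sections 3.3.2 and 4.1.3 can be read as scheduling instructions beside a definition in Section 4.1.3.1. That is fair. The fault is that the definition accepts forms which the instructions would treat as late.

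A reader might infer more than the text supports:

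- **Three conflicting cut-offs.** The annex definition only ties the Section 4.1.3.1 limit to the first participant. The conflict is between two events, enrolment and injection. No passage says that a selected site had already given the product to other patients.
- **Baseline follows arm-specific training.** Section 4.1.1 says study training includes "study procedures, and information and/or training on implementation strategies", given among other occasions at the investigator meeting and site initiation visits. It describes training for all SSPs. Section 4.1.2 mentions DI toolkit training without timing it. The 1-2 week target does not say before or after initiation, and Section 3.3 orders randomization only against participant enrolment. Arm-specific training before baseline is possible but not stated.
- **No baseline precedes the intervention.** The text guarantees no such order for the Sexual Health Assessment, but it does not exclude it, and facilitation is expressly held back.

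It can also be said that the tool is optional for site staff and completed by patients (Section 4.1.2), so an effect on staff FIM is conjecture, and that change from baseline carries no hypothesis test. Both stand as limits on the consequence. They do not remove it: Table 2 names feasibility as an outcome of the tool, Section 5.3 plans an analysis of change, and Section 5.4 plans SSP analyses by study arm.

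**Conclusion.** The point holds in a limited form. The protocol has two inconsistent limits for the SSP baseline, which can be 28 days or more apart under the conditions shown, and it exempts one DI-only component from the hold it places on facilitation. The accepted baseline for the secondary change in SSP FIM, AIM and ISQ can therefore follow the start of a DI component in one arm.

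Neither the size nor the sign of any bias can be derived from the documents. It depends on how many DI staff complete the form after the tool starts and on what the tool does to their ratings, and neither is given.

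A reader might infer that the main result is at risk. It is not: the primary endpoint is the mean FIM at Month 13, Section 5.1 tests that mean with clinic volume as the stratification factor, and no baseline adjustment is stated. The point is worth correcting because a later analysis plan cannot recover a baseline taken too late.

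**What to change.** 1. Use one cut-off in Sections 3.3.2, 4.1.3 and 4.1.3.1 and in the staff blocks of Annexes 1 and 2: SSP baseline FIM, AIM and ISQ are completed before the first participant is enrolled at that site.
2. Extend the existing hold sentence in both annexes so that the Sexual Health Assessment, like facilitation, begins only after all SSP baseline questionnaires at that site are complete. Collection of aggregate clinic data can stay as it is.
3. At sites already initiated, flag baseline forms completed after first enrolment or after the Sexual Health Assessment began, and repeat the change analysis without them.

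I would not require baseline before all training on the strategies. Staff who have not been told what their strategy is may have nothing to rate.

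The cost is protocol wording, a possible delay of some days in launching the tool at DI clinics, and one repeated analysis. No instrument or sample size changes. Where the baseline window has already closed, only the flag and the repeated analysis are available.
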